### 3 Populations of Analysis

In accordance with guidance from the International Conference of Harmonization of Technical Requirements for Registration of Pharmaceuticals for Human Use (ICH) guideline ICH E9 Statistical Principles for Clinical Trials (1998), the following data sets will be used for all statistical analysis:

- The full analysis set (FAS) includes all randomized subjects who receive any study medication and have at least one post-Baseline.
- The per protocol set (PPS) includes all subjects in the FAS who receive at least 6 months of study drug and attend at least 6 scheduled visits, except for those who are excluded because of major protocol violations, where a major protocol violation is one that may affect the interpretation of study results (e.g., non-compliance with study medication requirements as evaluated using TTP488 plasma concentration below the limit of quantification at last study visit during 18-month treatment period). The intended criterion of “6 scheduled visits” includes screening and baseline and at least 4 scheduled clinic visits after first dose of study medication.

Final determinations of the PPS will be made at the masked data review meeting (BDRM) held in accordance with ICH E9 prior to the lock data. The complete specification (made blinded to treatment arm) will be documented in the minutes to the blind data review meeting held prior to lock the data.

- The safety set (SAF) includes all subjects who receive any study medication.

For the purpose of understanding the influence of dropouts on study conclusions, the FAS will be partitioned into subjects who complete (completers) and subjects who do not complete (dropouts). For purposes of this study, a subject is a completer if the subject has received treatment for 18 months and has efficacy data for 18 months (evaluation is made at the endpoint level, so if a subject is missing ADAS-cog at Month 18 but has CDR-sb at Month 18, this subject is included in analyses for which the data are available).

It is noted that if the FAS and PPS do not differ by more than 15% in numbers of individuals, analysis may be limited to the FAS (ITT analysis), and the PP analysis will not be conducted.

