#### **4.1.4 Other Efficacy Variables of Analysis**

Additional efficacy variables of analysis are as follows:

- Responder analysis at Months 3, 6, 9, 12, 15 and 18 based on ADAS-cog (increase from baseline of 7 points or more) and responder analysis at Months 3, 6, 12, and 18 based on the CDR-sb (increase from baseline of 1 point or more). It is noted that a responder is a subject who has not declined, and thresholds are used for classification of having declined.
- Change from Baseline in ventricular volume at Month 18.
- Change from Baseline in whole brain volume at Month 18.
- Time to loss of one global stage on the Clinical Dementia Rating (CDR) score through Month 18.
- Change from Baseline on the ADAS-cog at Months 3, 6, 9, 12 and 15 and at Months 3, 6 and 12 for the CDR-sb and CDR subscale scores.
- Individual item responses on the Resource Utilization in Dementia (RUD) questionnaire and the total caregiver time spent assisting the patient based on the RUD at Months 6, 12, and 18.
- Proportion of participants who enter intermediate or long-term residential care (RUD) at Months 6, 12, and 18.
- Change from Baseline in the Dementia Quality of Life (DEMQOL) - Proxy total score at Months 6 and 12.
- Change from Baseline in the Neuropsychiatric Inventory (NPI) total score and subscale scores at Months 3, 6 and 12.
- Change from Baseline on the Mini-mental State Examination (MMSE) total score at Months 3, 6 and 12.
- Change from Baseline on the Continuous Oral Word Association Task (COWAT) score at Months 3, 6 and 12.
- Change from Baseline on the Category Fluency Test (CFT) score at Months 3, 6 and 12.
- Change from Baseline on the Trail Making Test (Versions A and B) time at Months 3, 6 and 12.

- Change from Baseline in the extent of brain glucose hypometabolism at Month 18.
- Change from Baseline in the severity of brain glucose hypometabolism at Month 18

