##### 4.1.5.1 Alzheimer's Disease Assessment Scale - Cognitive Subscale 70 point (ADAS-cog):

- Range: The scale range is 0 to 70 with higher scores indicating greater cognitive impairment.
- Brief description: The ADAS-cog is a structured scale (approximately 40 minutes to complete) that evaluates memory, orientation, attention, reasoning, language and constructional praxis (Rosen, 1984). The ADAS-cog scoring range for the version used in this study is from 0 to 70. The ADAS-cog will be conducted at Baseline and at Months 3, 6, 9, 12, 15 and 18 or in the event of early termination. The ADAS-cog should always be administered prior to other cognitive measures.

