#### **4.1.5.6 Clinical Dementia Rating Scale (CDR):**

- Global CDR Range:
  - 0 = normal; healthy individuals
  - 0.5 = questionable dementia
  - 1 = mild dementia
  - 2 = moderate dementia
  - 3 = severe dementia.
- CDR sum-of-boxes (CDR-sb) range: CDR-sb scores range from 0 to 18 with higher scores indicating greater cognitive impairment.
- Brief description: The CDR scale is used as a global measure of dementia and is completed by a clinician in the setting of detailed knowledge of the individual patient collected from interviews with the patient and caregiver ([Berg, 1988](#)). The CDR describes 5 degrees of impairment in performance on each of 6 categories including memory, orientation, judgment and problem solving, community affairs, home and hobbies, and personal care. Much of the information will therefore already have been

gathered, either as part of normal clinical practice or as part of a research study. The interview takes approximately 40 minutes to administer.

The scores for each category can also be summed and this is known as the sum of box score (CSR-SB). The CDR will be conducted at Baseline and at Months 3, 6, 12 and 18 or in the event of early termination. To avoid patient fatigue, the CDR should be performed on a separate visit day than the other cognitive tests.

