- First, for patients with intermittent missing values, before performing the MI, a monotone missingness pattern will be created. Intermittent missing values will be imputed using the Markov Chain Monte Carlo (MCMC) methodology which assumes a multivariate normal distribution over all variables included in the imputation model. The imputation model will be performed by treatment group and will include age, sex, ApoE status, education level, body weight (or BMI), baseline stratum, baseline and observed values at Months 3, 6, 9, 12, 15 and 18. Months 9 and 12 are not included in the model for endpoints which were not scheduled to be assessed at those visits. The MI procedure in SAS will be used for this purpose and this first MI step is planned to be repeated 100 times, creating several different datasets with a monotone missing data structure. A unique seed value will be used in the MI procedure and documented to allow for replication. The imputation is based on the missing at random (MAR) assumption, i.e. the missing data are assumed to follow the same model as the other patients in their respective treatment arm.
- After this, the remaining missing data will be imputed using a method for monotone missingness, also based on the MAR assumption. Thus, for each of the 100 created datasets with a monotone missing data pattern, the MI procedure in SAS will be used to impute missing values based on a sequential procedure reflecting the monotone missing data pattern. A seed value of 446786 will be used for this second invocation of the MI procedure. Patients with the first missing value occurring at Month 3 will have their missing Month 3 value replaced by an imputed value from a regression model by treatment group with age, sex, ApoE status, education level, BMI, baseline stratum, and baseline as potentially predictive variables.
- In the next step, patients with the first missing value occurring at Month 6 will have their missing Month 6 value replaced by an imputed value from a regression model with Month 3 data, in addition to the variables listed above.
- The same procedure will be repeated for all other visits.

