- The imputed datasets generated with the approach described above do contain only non-missing values and are used as input in the model for the supportive analysis of the primary endpoint. MMRM models similar to what are described above will thus be run on each of the generated imputed datasets and the difference between the treatment groups at Month 18 will be estimated. The MMRM model will be similar to the primary analysis. Finally, the MIANALYZE procedure in SAS will be applied to combine the results from these several datasets to derive an overall estimate of the treatment difference at Month 18. In addition to the estimates, corresponding 95% confidence intervals and p-values will be calculated.

Another MI analysis will be performed with the assumption that the data in the active treatment group are missing not at random (MNAR). A tipping point-based assumption will be used, i.e. the trajectories of the patients in the active treatment group after withdrawal are assumed to be worse by an amount of delta. After the MI using the MAR assumption, as defined above has been done, the amount of delta will be added to each imputed value in the active treatment group. Successively harsher deltas will be imposed on the imputed values in the active group, starting with an ADAS-cog increment (worsening) of 0.25 points or a CDR-sb increment

(worsening) of 0.1 points. The delta is further increased in the steps of 0.25 points (e.g., 0.50, 0.75) for ADAS-cog or in the steps of 0.1 points (e.g., 0.2, 0.3) for CDR-sb until the statistical significance is lost, i.e., until the p-value becomes more than 0.049. For the placebo group, the MI using MAR assumption will be used.

Further MI analysis assuming MNAR will be done using the Copy Reference approach. Placebo-group based assumption will be used, i.e. the trajectories of the patients are assumed to follow the placebo group after the discontinuation. Methods similar to those described above will be used to generate monotone missing data. After this, the missing data will be imputed sequentially for each visit (e.g., Month 3, Month 6). Only the data from the placebo group will be used for the imputation.

For the ANCOVA models, data from baseline and Month 18 will be used. Analysis will include treatment, baseline stratum as fixed factors and Baseline as covariate. For the LOCF analysis, the last available measurement will be used to impute the Month 18 data in case of missing data.

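### Supportive multiple imputation of CDR-sb uses no post-baseline ADAS-cog, so it can be modestly biased if ADAS-cog-related dropout differs between arms

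*SAP*

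**What the plan says.** SAP 5.2.1 plans multiple imputation (MI) as a supportive analysis, in two steps.

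- **Intermittent gaps (MCMC, by arm).** The model "will include age, sex, ApoE status, education level, body weight (or BMI), baseline stratum, baseline and observed values at Months 3, 6" and at the later visits.
- **Remaining gaps (sequential regression).** A missing Month 6 value, for example, has its "value replaced by an imputed value from a regression model with Month 3 data, in addition to the variables listed above".

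The model is built endpoint by endpoint, as the visit rule shows: "Months 9 and 12 are not included in the model for endpoints which were not scheduled to be assessed at those visits". Neither step names another outcome scale. The only ADAS-cog information in the CDR-sb model is the two-level screening stratum (19 or less, more than 19; SAP 1.4).

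The two scales have different schedules. SAP 4.1.5.1: "The ADAS-cog will be conducted at Baseline and at Months 3, 6, 9, 12, 15 and 18". SAP 4.1.5.6: "The CDR will be conducted at Baseline and at Months 3, 6, 12 and 18 or in the event of early termination". SAP 4.1.4 lists the secondary time points in the same way: "Change from Baseline on the ADAS-cog at Months 3, 6, 9, 12 and 15 and at Months 3, 6 and 12 for the CDR-sb".

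The tipping-point analysis starts from this imputation: "After the MI using the MAR assumption, as defined above has been done, the amount of delta will be added". Only imputed azeliragon values receive it. Copy-reference uses similar steps with placebo data only.

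**The concern.** Missing at random always means given the variables in the model. If patients leave because of decline that shows on the ADAS-cog, their missing CDR-sb values may be missing at random given both scales but not given CDR-sb history alone. The MI then imputes dropouts as if their latest cognitive result were unknown, although the trial has it.

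The gap is clearest after Months 9 and 15, where the last scheduled ADAS-cog is three months newer than the last scheduled CDR. ADAS-cog at Months 3, 6, 12 and 18 is left out as well. SAP 3, explaining that completer status is judged per endpoint, gives the case "if a subject is missing ADAS-cog at Month 18 but has CDR-sb at Month 18". In such a patient the scale that was observed would not inform the one that was not.

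At stake is what the sensitivity analyses for CDR-sb can show. The primary CDR-sb MMRM also conditions on CDR-sb history and no post-baseline ADAS-cog. Agreement between it and this MI therefore says little about dropout that follows the ADAS-cog.

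**Working it through.** **1. Inputs from the documents** (Protocol 9.1, repeated in SAP 1.6). CDR-sb: SD 2.4, difference 0.9. ADAS-cog: SD 9, difference 3.5. Two-sided alpha 0.05, power 90%, dropout 20% or less, about 400 randomized per sub-study.

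**2. The plan's own figures reproduce.** Per arm, n = 2(1.960 + 1.282)² (SD/difference)².

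- CDR-sb: 149.4, so 150 by the normal approximation and 151 by exact t; 152 stated. Power at 152 per arm is 0.903. 304/0.8 = 380, as stated.
- ADAS-cog: 138.96, so 139 and 140; 141 stated. Power at 141 per arm is 0.902. 141/0.8 = 176.25, rounded up to 177 per arm, or 354, as stated.

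The inputs are thus a sound base for the simulations. The documents give no figure for imputation bias.

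**3. Who has a newer ADAS-cog than CDR?** Assume dropout is even over the five intervals after Month 3. Those leaving after Month 9 or Month 15 are 2/5 = 40%. With 20% of 400 = 80 dropouts, that is 0.40 × 80 = 32 per sub-study. This counts scheduled CDRs only.

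**4. Bias in the Month 18 CDR-sb difference** (azeliragon minus placebo; negative favours azeliragon). All runs use the SDs, effects and visit schedules above and 20% dropout. The correlation between the scales at Month 18 is assumed. Moderate dependence means log-odds of dropout of 1 (about 2.7-fold odds) per SD, or per 9 points, of the latest ADAS-cog change, in one arm only.

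| Simulation | Correlation | Own-scale MI | ADAS-cog added |
|---|---|---|---|
| 200 per arm, azeliragon only | 0.53 | -0.040 | +0.023 |
| 200 per arm, azeliragon only | 0.68 | -0.084 | +0.003 |
| 200 per arm, placebo only | 0.53 | +0.068 | +0.006 |
| 200 per arm, placebo only | 0.68 | +0.090 | -0.001 |
| Large sample, azeliragon only | 0.60 | -0.056 | +0.005 |
| Large sample, azeliragon only | 0.75 | -0.067 | -0.003 |

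The rows with 200 per arm are means of 400 simulated trials with 10 imputations each (Monte Carlo error about 0.013). The large-sample rows use at least 200,000 per arm.

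- **Same mechanism in both arms:** own-scale bias within ±0.012.
- **Early-termination CDR:** with azeliragon-only dropout and correlation 0.53 to 0.69, bias favouring azeliragon is 0.07 to 0.10 with no such CDR. It is 0.04 to 0.08 if 80% of dropouts have one (assumption). Where it falls depends on whether the nearest scheduled visit means any visit or only a CDR visit.
- **Other strengths:** with log-odds from 0.5 to 4.0 per 9 points and correlation 0.37 to 0.75, the bias runs from 0.02 to 0.21. The upper end needs very strong one-arm dependence.

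**5. Size in context.** For 0.04 to 0.10 points:

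- share of the planned effect: 0.04/0.9 = 4%; 0.10/0.9 = 11%
- share of a standard error, 2.4 × √(2/160) = 0.268: 0.04/0.268 = 0.15; 0.10/0.268 = 0.37
- shift of the tipping delta: with 20% of the active arm imputed, a delta moves the difference by 0.2 × delta, so the shift is 0.04/0.2 = 0.2 to 0.10/0.2 = 0.5, or two to five steps of 0.1 (standard error taken as unchanged).

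**The case against.** The case against acting is substantial, and much of it stands.

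- **The model is not bare.** It holds age, sex, ApoE, education, weight or BMI and the screening ADAS-cog stratum. What it lacks is post-baseline data from the other scale.
- **MI is supportive.** Success is p < 0.049 in the primary analysis for both endpoints in both sub-studies (SAP section on adjustments for multiplicity). LOCF, completers, observed-cases and rank analyses are also planned. A reader might infer that the gap inflates the trial's type I error or invalidates the CDR-sb result. The documents do not support that: no success criterion uses the MI.
- **Early-termination data help.** CDR is collected at that visit if it falls within 30 days of last dose (Protocol 6.3) and is mapped to the nearest scheduled visit (SAP 6.5). This shrinks the bias but does not remove it, and Months 9 and 15 have no scheduled CDR to map to.
- **The tipping point already probes the drug-favouring direction.** It makes active-arm dropouts worse until significance is lost. This stands. What remains is a starting point displaced by a few steps. The placebo-driven direction is not probed, but there the MI understates benefit.
- **The mechanism is assumed.** Protocol 1.1.3 reports cognitive worsening at 20 mg/day in Phase 2 but not at 5 mg/day or placebo. The documents do not show that dropout here will follow the ADAS-cog in one arm.
- **SAP 3 gives a hypothetical.** It does not show that many patients will have only one co-primary at Month 18.
- **Adding a second scale complicates the scheme.** Monotone order, the delta and copy-reference all need a rule. Each can be given in a sentence, as below.

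**Conclusion.** The point holds as a modest, conditional weakness in a supportive analysis. The CDR-sb imputation leaves out all post-baseline ADAS-cog. Under moderate one-arm dependence and 20% dropout, the estimated difference is off by roughly 0.04 to 0.10 points. It favours azeliragon if the mechanism acts in that arm and goes against it if it acts in placebo.

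This rests on three assumptions: the correlation between the scales, the strength of the dependence, and its restriction to one arm. Without a difference between arms the bias is about zero. Reading the gap as a general bias in the CDR-sb results would go too far. It is still worth closing, because the data are already collected and the analysis exists to test robustness to missing data.

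**What to change.** In SAP 5.2.1, before unblinding:

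- When imputing CDR-sb, add ADAS-cog at Months 3, 6, 9, 12, 15 and 18 as auxiliary variables. When imputing ADAS-cog, add CDR-sb at Months 3, 6, 12 and 18. Keep imputation by arm.
- Order both scales' variables by visit so that dropout stays monotone. Let the MCMC step fill intermittent gaps, including one scale missing at a visit where the other was observed.
- Base the tipping-point analysis on this model, adding delta to each scale only after the MAR imputation is complete.
- For copy-reference, fit the same model on placebo and apply it to each patient's own observed history.

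The visit rule in that paragraph can be corrected at the same time. It names Months 9 and 12, whereas the CDR schedule omits 9 and 15. This is a separate wording matter.

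The cost is SAP text, some extra programming and a larger imputation model: up to about ten more predictors with about 200 patients per arm. The primary MMRM does not change.

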Interaction terms will be examined in supportive analyses. In the event of a significant interaction term, the impact on analysis conclusion will be examined. The primary model will not include interaction terms. A key supportive analysis will use the ITT methodology and a main-effects model for ANCOVA adjusting for baseline ADAS-cog (CDR-sb) using last-observation-carried-forward (LOCF) methods for missing data, justified based on known profiles of ADAS-cog (CDR-sb) in AD patients, which is conservative under the assumption that there are not more dropouts in the active-treated group than the placebo group. Rank ANCOVA will be done as a supportive analysis.

To ensure robustness of analysis conclusions against missingness, multiple imputation methods will also be done to cope with missing data as a key supportive analysis using the final on-treatment assessment of treatment failures as non-missing data at endpoint.

In accordance with the recommendations of the report from the National Academy of Science (NAS) panel “*The Prevention and Treatment of Missing Data in Clinical Trials*,” (National Research Council, 2010), missingness is classified as “missing at random” (MAR) or “missing not at random” (MNAR). When subjects are withdrawn due to treatment failure, this event is considered in this sensitivity analysis to be MNAR, and the endpoint value is taken as the hard endpoint (not imputed) in analysis, operationally, the endpoint analysis is the same as LOCF. Data that are missing for other reasons are considered to be MAR, and standard multiple imputation methods are planned.

Descriptive summaries will be produced of the observed values and change from Baseline in co-primary variables by treatment group at each individual time point and at endpoint (final on-treatment assessment for each subject).

For statistical analyses, 95% confidence intervals will be produced for the least-squares means (LSM) in each treatment group, as well as the LSM differences as compared to placebo plus SoC. For MMRM and ANCOVA, two-sided p-values will be displayed for the comparison against placebo plus SoC.

Because there are limited numbers of subjects per center, there will be inadequate power to explore impact of the center effect on study conclusion. Descriptive statistics by center will be presented.

The primary analysis controls alpha through the conditional sequence of hypothesis testing. No further adjustment for multiplicity is necessary.

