### **5.2.1 Statistical Methodology for Primary Efficacy Analysis**

The primary analysis will be done on change from baseline in ADAS-cog and on change from baseline in CDR-sb.

The primary analysis will use the ITT methodology and a main-effects (for covariates) mixed-models for repeated measures (MMRM) methodology. The MMRM will utilize an unstructured covariance where the number of parameters is  $t(t+1)/2$  where  $t$  is the dimension of the covariance matrix, using PROC MIXED in SAS. In the unlikely event of lack of convergence, Toeplitz structure will be employed where the number of parameters is  $t$  where  $t$  is the dimension of the covariance matrix. Time is considered as a class variable. Analysis will include treatment, time, treatment-by-time interaction, Baseline as covariate, and baseline stratum as a covariate, and subject as a random effect (acknowledging that subject is a source of random variation). This method provides the primary treatment comparison at Month 18. Supportive modeling will also include MMRM main-effects model with treatment, time, and subject.

The primary analysis will also be done on randomization stratification subgroups defined by (1) baseline ADAS-cog 19 or less and (2) baseline ADAS-cog more than 19.

Multiple imputations (MI) will be used as an alternative for coping with missing data as supportive analyses with 100 invocations (acknowledging that more invocations are needed with more missing data). Monte Carlo methods are planned.

The MI analysis assuming Missing at Random (MAR) will be done as follows:

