Rank analogues (e.g., Wilcoxon analysis, rank ANCOVA, and van Elteren analysis when strata are a part of the approach) will be used for additional supportive analyses. An observed-cases analysis will be done by visit.

An essential component of the thorough analysis includes an assessment of the impact of missing data on study conclusions. As a part of assessing this impact, sensitivity analysis will include an endpoint analysis (reduction to last-observation-carried-forward, justified in this study based on the monotonic progression of the natural course of AD and assuming no more dropouts in the group treated with azeliragon plus SoC than in the group treated with placebo plus SoC), a completers analysis (observed cases at Month 18), and observed cases by assessment time.

Interaction terms will be examined in the supportive analyses. The primary model will not include interaction terms with covariates. In the event of a significant interaction term, the impact on analysis conclusion will be examined. A key sensitivity analysis will use the ITT methodology and a main-effects model for ANCOVA adjusting for baseline ADAS-cog (CDR-sb) using last-observation-carried-forward (LOCF) methods for missing data, justified based on known profiles of ADAS-cog (CDR-sb) in AD patients, which is conservative under the assumption that there are not more dropouts in the active-treated group than the placebo group. Rank ANCOVA will be done as a supportive analysis.

Additional unplanned sensitivity analyses may be performed.

Descriptive summaries will be produced of the observed values and change from Baseline in co-primary variables by treatment group at each individual time point and at endpoint (final on-treatment assessment for each subject).

For statistical analyses, 95% confidence intervals will be produced for the least-squares means (LSM) in each treatment group, as well as the LSM differences as compared to placebo plus SoC. For MMRM and ANCOVA, two-sided p-values will be displayed for the comparison against placebo plus SoC.

Because there are limited numbers of subjects per center, there will be inadequate power to explore the impact of the center effect on study conclusion. Descriptive statistics by center will be presented.

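### The primary MMRM allows one baseline slope for all visits, which may cost some precision at Month 18 if the true slope changes over time

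*SAP*

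**What the plan says.** SAP 5.2.1 sets out the model: "The primary analysis will use the ITT methodology and a main-effects (for covariates) mixed-models for repeated measures (MMRM) methodology". Its terms follow: "Analysis will include treatment, time, treatment-by-time interaction, Baseline as covariate, and baseline stratum as a covariate", with subject as a source of random variation. It adds "Time is considered as a class variable" and "The MMRM will utilize an unstructured covariance where the number of parameters is" t(t+1)/2. Later in the same section comes the restriction "The primary model will not include interaction terms with covariates". Baseline-by-visit is such a term, so it is excluded.

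Protocol 9.5.2 is broader: "The primary model will not include interaction terms". Read literally, that would also exclude the treatment-by-time term which the same section lists. The SAP wording resolves this.

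The visits in the ADAS-cog model come from SAP 4.1.5.1: "The ADAS-cog will be conducted at Baseline and at Months 3, 6, 9, 12, 15 and 18 or in the event of early termination". SAP 4.1.5.6 gives Months 3, 6, 12 and 18 for the CDR. The primary treatment comparison is at Month 18 only.

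SAP 5.2.1 also plans supportive work that bears on the point:
- a look at interaction terms, with the terms not named;
- ANCOVA using baseline and Month 18 data, including an LOCF version;
- a Month 18 completers analysis;
- multiple imputation by visit and by treatment group, with baseline as a predictor.

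**The concern.** Visit means, treatment effects and the covariance are all left free over time. Baseline and stratum are not: each has one coefficient across six ADAS-cog visits or four CDR-sb visits. If baseline predicts change differently at Month 18 than at Month 3, the common slope is a compromise that need not fit at the one visit that decides the trial. Two things could be at stake:
- **Precision.** Baseline variation left unexplained at Month 18 goes into the residual.
- **Robustness.** If patients who leave differ in baseline severity between arms, the misfit may no longer cancel in the treatment difference.

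**Working it through.** **1. The plan's own figures.** Protocol 9.1 gives SD 9 and difference 3.5 (ADAS-cog), SD 2.4 and difference 0.9 (CDR-sb), 90% power, a two-sided two-sample t-test at alpha 0.05, and 20% dropout. By n per arm = 2(z₁₋α/₂ + z₁₋β)²σ²/δ²:
- ADAS-cog: 2 × (1.960 + 1.282)² × 81/12.25 → 139
- CDR-sb: 2 × (1.960 + 1.282)² × 5.76/0.81 → 150

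The exact t-test gives 140 and 151 at alpha 0.05, and 141 and 152 at 0.049. The stated 141 and 152 are therefore reproduced (power 90.2% and 90.3% at 0.05). Dropout: 282/0.8 = 352.5, stated as 354; 304/0.8 = 380, as stated. These figures use no covariate, so they do not depend on the term in question.

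**2. The mechanism.** With T for treatment, B for baseline and S for stratum, the SAP fits mean change at visit j as μⱼ + τⱼT + βB + γS. The alternative uses βⱼ and γⱼ. If the true Month 18 slope is β₁₈, the SAP model leaves (β₁₈ − β)B in the residual. With complete data:

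variance inflation = (β₁₈ − β)² × Var(B) / σ²

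Randomization makes B independent of T, so the leftover term has the same mean in both arms and the contrast stays unbiased.

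**3. Size by formula, ADAS-cog.** The documents give no slope or baseline SD, so both are assumed: baseline SD 5 to 8, with residual SD set to 9.
- Gap 0.1, SD 5: 0.01 × 25/81 = 0.3%
- Gap 0.3, SD 8: 0.09 × 64/81 = 7.1%
- Gap 0.5: 0.25 × 25/81 = 7.7% to 0.25 × 64/81 = 19.8%

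With 141 per arm, residual SD 9 and alpha 0.049, power moves from 90.1% to between 90.0% and 88.0% for gaps of 0.1 to 0.3, and to between 87.8% and 84.3% for a gap of 0.5.

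**4. Size by simulation.** The SAP's MMRM was compared with the same model plus baseline-by-visit and stratum-by-visit. Settings: N = 400, 1:1 stratified, about 20% MAR dropout depending on baseline alike in both arms, alpha 0.049, 3000 runs per scenario (Monte Carlo SE of power √(0.95 × 0.05/3000) ≈ 0.4 points). Assumed: baseline SD 6.5 (ADAS-cog) and 1.6 (CDR-sb), slope changing linearly from Month 3 to Month 18, visit SD rising from half to full by Month 18, adjacent-visit residual correlation 0.75.

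| Slope, Month 3 to 18 | Variance ratio, model-based | Variance ratio, empirical | Power, one slope | Power, by visit |
|---|---|---|---|---|
| ADAS-cog, equal (0.1) | 1.00 | 1.00 | 94.7% | 94.7% |
| ADAS-cog, 0 to 0.2 | 1.02 | 1.01 | 94.9% | 95.0% |
| ADAS-cog, 0 to 0.4 | 1.06 | 1.03 | 95.0% | 96.0% |
| ADAS-cog, −0.2 to 0.4 | 1.15 | 1.08 | 93.5% | 96.0% |
| CDR-sb, 0 to 0.4 | 1.05 | 1.03 | 93.1% | 94.0% |
| CDR-sb, −0.2 to 0.6 | 1.24 | 1.14 | 92.4% | 95.9% |

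No equal-slope CDR-sb case was run; by the formula in step 2 its loss is zero. The empirical ratio is below the model-based one because the common-slope standard error is slightly conservative when slopes change (ADAS-cog, −0.2 to 0.4: model 1.002, empirical 0.982). A separate simulation (500 trials per scenario, baseline SD 7, slope rising to 0.3 or 0.5) gave ADAS-cog standard errors of 0.952 against 0.936 and 0.938 against 0.894, which are variance ratios of 1.03 and 1.10. Short 300-run checks of the steepest ADAS-cog case with baseline SD 8 or correlation 0.9 gave ratios of 1.22 to 1.25, so the upper end depends on these assumptions.

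**5. All four tests together.** SAP 5.2.1/5 requires p < 0.049 on both endpoints in both sub-studies. Joint power is (P_ADAS × P_CDR)² if the endpoints are independent and the smaller power squared if they are fully correlated.
- Slopes 0 to 0.4 for both: (0.950 × 0.931)² = 78.2% against (0.960 × 0.940)² = 81.4%; or 0.931² = 86.7% against 0.940² = 88.4%.
- Steepest slopes for both: 74.6% against 84.8%; or 85.4% against 92.0%.

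**6. Bias.**

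| Dropout | One slope | By visit |
|---|---|---|
| Depends on baseline alike in both arms | bias about 0; type I error 4.0-5.0% | bias about 0; 4.9-5.2% |
| Depends on baseline in the active arm only, slopes changing | bias towards the drug: 0.18-0.49 (ADAS-cog), 0.09-0.17 (CDR-sb); type I error 5.7-8.3% | bias about 0; 4.8-5.1% |
| As above, slopes equal (ADAS-cog) | bias about 0; 4.7% | bias about 0; 5.1% |

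Against the planned differences, the biases are 0.18/3.5 = 5% to 0.49/3.5 = 14%, and 0.09/0.9 = 10% to 0.17/0.9 = 19%. Exchanging the arms would reverse the sign.

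**The case against.** A main-effects covariate model is a consistent, prespecified choice, and the contrast is unbiased under randomization with complete data. The documents contain no baseline slope, baseline SD or correlation, so no loss is demonstrated. Sizing took no credit for covariate adjustment and about 400 per sub-study exceeds the 354 and 380 needed; even in the steepest simulated cases the common-slope model kept 93.5% and 92.4% power. Bias needs three conditions at once: changing slopes, baseline-dependent dropout, and a difference between arms in that dependence. Nothing in the documents indicates that pattern. All of this stands.

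The planned supportive analyses also count. The imputation regressions allow visit- and arm-specific baseline slopes, which addresses the bias route directly, and the Month 18 ANCOVA estimates its own Month 18 slope. It would be wrong to infer that nothing in the plan tests the assumption. But the interaction check does not name baseline-by-visit, the ANCOVA relies on LOCF or completers, and the imputed data go into an MMRM like the primary one. None of these changes the deciding p-value.

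The change is also more than a wording edit. SAP 5 treats the primary analysis as fully specified by the protocol, and SAP 6.2 says primary methods following the ITT principle will not change. That is a reason to document the change properly.

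**Conclusion.** The exclusion is real and applies to both co-primaries. Its cost is conditional: essentially none if baseline slopes are equal across visits, and about 0-15% (ADAS-cog) or 5-24% (CDR-sb) more model-based variance in the main simulated scenarios, or about 0-3.5 power points per test. The loss is larger for the joint criterion if both endpoints have steeply changing slopes. Slopes, baseline SDs and correlations are all assumptions.

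A reader might infer that the trial is underpowered or that the primary estimate is biased. The documents support neither. The stated sample size and 90% power come from an unadjusted t-test and are unaffected, and bias arises only in the deliberately adverse dropout case of step 6. The case for change is that visit-specific slopes gain when slopes differ and lose essentially nothing when they do not.

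**What to change.** Before unblinding:
- Add baseline-by-visit to the primary MMRM for ADAS-cog and CDR-sb and, for the same reason, stratum-by-visit.
- Reword the restriction in SAP 5.2.1 so that it bars only treatment-by-covariate interactions.
- List the change in SAP 1.9, which now records only the dropping of the Bazett correction, and align the sentence in Protocol 9.5.2.

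The cost is 5 extra parameters per covariate for ADAS-cog (six visits) and 3 for CDR-sb (four visits), with about 400 patients per sub-study, plus a documented change to the SAP and protocol model. No new data are needed. If the sponsor keeps the present primary model, the by-visit model should at least be named as a prespecified sensitivity analysis, though that would leave the primary test as it is.
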